1. BACKGROUND INFORMATION

1.1. Polycystic Kidney Disease

Polycystic kidney disease (PKD) is the most common inherited kidney disease in the United States, occurring in approximately 1 in every 1,000 live births. It affects more than 600,000 people in the United States and 12 million worldwide ². It is the third most common single cause of kidney failure.

Polycystic kidney disease is characterized by the growth of numerous renal cysts, which cause abnormalities in both structure and function of the kidneys. Cysts also develop in other organs, particularly in the liver. Other manifestations of PKD include high blood pressure, urinary tract infections, kidney stones, hematuria, and aneurysms. Pain in the back, abdomen, and pelvis affects many PKD patients.

There are 2 types of PKD, autosomal dominant (ADPKD) and autosomal recessive (ARPKD). In the more common form, ADPKD, the abnormal PKD gene (polycystin 1 or 2 [*PKD1* or *PKD2*]) is inherited from 1 parent who also has PKD. Affected individuals become aware of the disease at varying times from childhood to adulthood. If a family history exists, individuals are assessed regularly for manifestations of the disease. Others may have cysts detected during routine medical evaluations for hematuria or hypertension or an ultrasound examination for other medical symptoms and conditions. There is, however, a small percentage of people with ADPKD who do not have a family member with the disease. Autosomal recessive PKD is associated with abnormal function of the kidneys and liver, and is usually diagnosed by ultrasound during fetal development or shortly after birth. Unlike ADPKD, a mutant *PKHD1* gene must be contributed by each parent in order for ARPKD to occur in an offspring. Parents are usually unaware of being carriers of the mutant gene because they are asymptomatic.

In ADPKD, the mutation in either the *PKD1* or *PKD2* gene results in the abnormal, uncontrolled growth of renal tubular epithelial cells ³. Epithelial growth factor receptor (EGFR) is overexpressed and mislocated from the basolateral to the luminal surface of renal tubular cells ⁴. Epithelial growth factor receptor ligands are secreted by tubular cells and are found in human PKD cyst fluids. The combination of EGFR mislocation and ligand secretion establishes an autocrine loop resulting in persistent renal tubular cell proliferation ⁵. Chronic proliferation results in renal cyst formation ⁶. The cysts then cause a structural distortion of the renal architecture, impeding normal nephron function. Cyst enlargement results in a massive increase in kidney volume and a progressive impairment of renal function ⁷. Associated clinical symptoms include hypertension, recurrent flank pain, hematuria, and recurrent pyelonephritis. Currently, there are no disease-modifying therapies for ADPKD; all existing treatment strategies are palliative and aimed at controlling symptoms ⁸.

1.2. Tesevatinib

Tesevatinib (formerly named XL647 and KD019) is a new chemical entity that inhibits

multiple tyrosine kinases (TKs) (ErbB family members [EGFR and human epidermal growth factor receptor 2], vascular endothelial growth factor receptor 2/kinase insert domain receptor [VEGFR2/KDR]), and Src family kinases.

Nonclinical Toxicology

Tesevatinib nonclinical toxicology has been characterized in multiple species using a variety of dosing regimens. Details can be found in the Investigator's Brochure.

Clinical Experience with Tesevatinib

Tesevatinib has been evaluated in over 350 subjects, including 232 subjects with solid tumor malignancies in 3 Phase 1 studies, 4 Phase 2 studies, and 1 Phase 3 study; 66 healthy subjects in 4 clinical pharmacology studies; and 73 subjects with PKD (Study KD019-101).

1.2.1.1. Tesevatinib in Oncology Indications

Details on completed and ongoing studies of tesevatinib in oncology indications, including advanced solid tumors, non-small cell lung carcinoma, breast cancer, and glioblastoma can be found in the Investigator's Brochure.

Adverse events of special interest as of the data cutoff of October 2016 are described below.

Diarrhea and Rash

Diarrhea and rash were both expected as they are a class effect of all EGFR inhibitors.

At 150 mg QD, 3 of 5 patients had moderate rash occurring during the first 28 days, the event led to study discontinuation in 2 of the patients. The tolerability of intermittent dosing schedules using 150 mg (Monday, Wednesday, and Friday or Monday and Thursday) was

^a Includes 9 subjects from Cohort 1 and 15 subjects who were enrolled in the Phase 2a portion of the study.

^b One subject did not have a baseline TKV value.

improved over 150 mg QD, but 1 case of severe rash occurred in a patient receiving 150 mg on Monday and Thursday. While rash at the 150 mg dose level did not meet strict safety criteria for defining the maximum tolerated dose (MTD), this dose level was considered intolerable for long-term administration in this population. Therefore, the MTD for daily dosing was determined to be 100 mg daily.

Creatine Phosphokinase Elevations

There were 41 subjects with elevations of CPK above the normal range in Study KD019-101. Ten subjects experienced moderate CPK elevation (> 2.5 × upper limit of normal [ULN] – 5.0 × ULN), and 7 subjects experienced severe CPK elevation (> 5.0 × ULN). Quantitative whole body radiography in rats indicates relatively low accumulation of tesevatinib in skeletal muscle. In Study KD019-101, muscle AEs correlated poorly with CPK levels. While elevations of CPK commonly occur with exercise, the lack of a control group in Study KD019-101 makes it difficult to fully evaluate the relationship between tesevatinib and CPK elevations.

Amylase Elevations

In summary, mild asymptomatic increases in amylase levels have been seen frequently in Study KD019-101, including in subjects in the 50 mg daily cohort, and appear to be due to increases in pancreatic amylase. Subjects with baseline elevations in amylase are no longer eligible for tesevatinib ADPKD studies. If amylase levels rise to 1.5 × ULN, evaluation of lipase, amylase isoenzymes, and lipid levels are performed (see Section 7.5.6).

Serum Creatinine Elevations

The initial data indicate that subjects with ADPKD receiving tesevatinib have experienced elevations of creatinine without elevations in cystatin C. The median changes from screening values for creatinine and cystatin C from all subjects receiving the 50 mg dose reveal that creatinine values were increased by 11.1% at Day 3, by 14.3% at Day 7, and increased by 10% at Day 28. Data after Day 28, including several subjects who have received tesevatinib for 24 months, do not indicate any significant ongoing change in creatinine. During the same time period, cystatin C levels did not change (median decreases were 0%, 1.9%, and 1.7% at Days 3, 7, and 28, respectively). Data from the 8 subjects enrolled into the 100 mg dose cohort, as well as subjects enrolled in subsequent cohorts, exhibited a similar pattern. This increase in creatinine occurs early and after approximately 7 days, does not continue to increase, similar to the increase in serum creatinine seen with cimetidine. Increases in creatinine were seen in previous clinical studies of tesevatinib; however, most of the previous studies were in subjects with malignancies, and in previous studies, cystatin C levels were not evaluated, so increases in serum creatinine that may not represent renal dysfunction were not recognized.

QTc Prolongation

Safety conclusions from Study KD019-101 are that tesevatinib 150 mg in various schedules was associated with skin rash that was not well tolerated. While the MTD dose of 100 mg QD was based on criteria defined in the protocol, the occurrence of moderate QTc prolongation in 2 subjects dosed at that level led to a decision later in the study to recommend 50 mg QD as the best tolerated daily dose. Tesevatinib 50 mg QD appeared to be a well-tolerated dose in patients with ADPKD, although some acneiform rash occurred.

Further details on Study KD019-101 can be found in the Investigator's Brochure.

1.2.1.3. Clinical Pharmacokinetics

A preliminary noncompartmental analysis of tesevatinib pharmacokinetics (PK) from Phase 1 studies of intermittent dosing indicated that tesevatinib was rapidly absorbed following oral administration, with a median observed time to reach peak plasma concentration (T_{max}) of 4-8 hours. Area under the plasma drug concentration time curve (AUC) and the C_{max} generally increased approximately in proportion with dose over the full dose range (ie, 3.4 to 586 mg). Mean terminal half-life after 5 consecutive QD doses ranged from 50 to 92 hours, and appeared generally independent of dose. High inter-subject variability in exposure was observed with coefficient of variation (CV%) values of 46% and 43% for dose normalized C_{max} and AUC₀₋₂₄, respectively. Results from 5 subjects in the Phase 2 study who received 350 mg tesevatinib on the intermittent schedule showed that the concentration of tesevatinib appeared unchanged from cycle to cycle. These results suggest that tesevatinib does not accumulate significantly from one 14-day cycle to the next.

A preliminary noncompartmental PK analysis has been completed for 15 subjects given tesevatinib QD for at least 29 consecutive days. Tesevatinib was rapidly absorbed following oral administration (mean T_{max} ranged from 3.3 to 7.3 hours) and steady state appeared to have been reached by about Day 15. The estimated median accumulation ratio was 4.6 (accumulation ratio based on 300 mg QD dose). The median T_{max} at the MTD was 4 hours.

1.3. Study Rationale

Rationale for the ADPKD Indication

In nonclinical studies, tesevatinib selectively inhibited key kinases and validated targets in animal models of PKD. Results from nonclinical efficacy studies demonstrated that tesevatinib possesses significant potential to prevent the formation of cysts due to an increased proliferation of renal ductal epithelial cells. Nonclinical studies using 2 rodent models (BPK mouse and PCK rat) of PKD have demonstrated that tesevatinib reaches its target, the kidneys, and inhibits the signaling pathway for MEK/ERK by inhibiting the phosphorylation of EGFR (and Src, Erb2, VEGFR2/KDR). The decreased phosphorylation of EGFR and Erb2 contributes towards decreased proliferation of epithelial cells in the kidneys and reduces renal enlargement in these 2 disease models.

In summary, both the nonclinical and clinical results to date suggest that tesevatinib may be a promising therapeutic for ADPKD.

Rationale for Dosage Selection

Safety reviews after the first 2 cohorts in Study KD019-101 (50 mg QD and 100 mg QD) deemed these cohorts to have adequate safety and to be tolerable. In the 150 mg QD cohort, 3 of 5 subjects enrolled withdrew consent primarily due to concerns with rash. It was noted that all 5 subjects in this cohort experienced rash within the first 28 days of treatment. In comparison, 4 out of 9 subjects in the 50 mg cohort and 1 out of 8 subjects in the 100 mg cohort experienced rash within the first 28 days. While rash at the 150 mg dose level did not meet strict safety criteria for defining the MTD, this dose level was considered intolerable for long-term administration in this population. Therefore, the MTD for daily dosing was determined to be 100 mg QD. While the MTD dose of 100 mg QD was based on criteria defined in the protocol, the occurrence of moderate QT prolongation in 2 subjects dosed at that level led to a decision later in the study to recommend 50 mg QD as the best tolerated daily dose.

Study KD019-101 is currently enrolling additional subjects at the dose of 50 mg QD (SILK cohort) in order to increase the robustness of the safety data in subjects with ADPKD treated with tesevatinib.

2. STUDY OBJECTIVES AND PURPOSE

2.1. Primary Objective

The primary objective of this study is to evaluate the change from baseline in htTKV as measured by magnetic resonance imaging (MRI) at Months 12, 18, 24, and 30 days post-dose in patients with ADPKD treated with tesevatinib or placebo.

2.2 Secondary Objective

The secondary objective of the study is to evaluate the safety and tolerability of tesevatinib 50 mg QD in patients with ADPKD, and to also evaluate the change in eGFR using the MDRD-4 formula at the Month 12, 18, 24, and 30 days post-dose time points.

3. STUDY DESIGN

This is a Phase 2b, multicenter, double-blind, randomized, parallel group study to evaluate the change from baseline in htTKV as measured by MRI in subjects with ADPKD treated with tesevatinib or placebo. Male and female subjects with ADPKD, 18 to 60 years of age and with an eGFR \geq 30 mL/min/1.73 m² and \leq 80 mL/min/1.73 m² will be enrolled. Up to 100 male and female subjects will be randomized 1:1 to receive 50 mg of tesevatinib QD or placebo. The study will be conducted at approximately 25-30 sites in the United States.

Subjects will be screened up to 28 days before initiation of treatment with tesevatinib or placebo (certain screening assessments may be conducted up to 42 days prior to dosing). Screening assessments will include medical and PKD history, physical examination, vital signs, electrocardiograms (ECGs), clinical laboratory evaluation (including hematology, serum chemistry, coagulation, thyroid stimulating hormone, urinalysis, and pregnancy), ocular examination, echocardiogram, and MRI. Calculation of htTKV at screening for eligibility determination may be performed by a local radiologist.

Starting on Day 1, subjects will receive 50 mg QD of tesevatinib or placebo for up to 24 months. During the Early Treatment Period (Days 1 to 28), subjects will report to the study site on Days 1, 14, and 28; subjects will be followed every 28 days from Months 2 to 12 and every other month from Months 12 to 24. Safety assessments will be performed at regular intervals throughout the study and will include physical examinations, vital signs, ECGs, clinical laboratory evaluations, ocular examination and echocardiograms. Magnetic resonance imaging to determine the change from baseline in htTKV will be performed at Months 12, 18, and 24. Entry into the study will be based on local MRI readings, but central MRI readings and htTKV calculation will be performed at baseline and during the study.

All subjects will undergo an end-of-study evaluation approximately 30 days after the last dose of study drug.

4. STUDY POPULATION

4.1. Inclusion Criteria

Subjects will be included in the study if they meet all of the following inclusion criteria:

- 1. Confirmed diagnosis of ADPKD based on Ravine's criteria. Subjects < 30 years of age must have at least 2 cysts (unilateral or bilateral) while subjects ≥ 30 years of age must have at least 2 cysts in each kidney (ie, total ≥ 4 cysts).
- 2. Cysts must be at least 1 cm in size to be considered.
- 3. At least 18 years old and no more than 60 years old at the time of consent.
- 4. eGFR ≥ 25 mL/min/1.73 m² and ≤ 90 mL/min/1.73 m², using the Modification of Diet in Renal Disease-4 variable formula.
- 5. htTKV must meet the following criteria (htTKV is calculated using total kidney volume obtained from MRI divided by height in meters):
 - \geq 500 mL for subjects 18-35 years of age
 - > 750 mL for subjects 36-49 years of age
 - > 900 mL for subjects 50-60 years of age
- 6. Subject has the following laboratory values:
 - Platelets > lower limit of normal (LLN)
 - Hemoglobin > 9 g/dL
 - Total bilirubin $\leq 1.5 \text{ mg/dL}$
 - Aspartate aminotransferase < 2.5 × ULN
 - Alanine aminotransferase $< 2.5 \times ULN$
 - Prothrombin time/partial thromboplastin time $\leq 1.5 \times ULN$
 - International normalized ratio (INR) \leq 1.5, except those subjects taking warfarin who must have INR \leq 3
 - Albumin > LLN
 - Amylase $\leq 1.5 \text{ x ULN}$
 - Lipase $< 1.5 \times ULN$
 - Serum potassium within normal limits
 - Serum magnesium within normal limits
- 7. Female subjects of childbearing potential must have a negative pregnancy test at screening. Females of childbearing potential are defined as sexually mature women without prior hysterectomy, bilateral tubal ligation, or who have had any evidence of menses in the past 12 months. However, women who have been amenorrheic for 12 or

more months are still considered to be of child bearing potential if the amenorrhea is possibly due to prior chemotherapy, anti-estrogens, or ovarian suppression.

- Women of childbearing potential must have a negative urine pregnancy test (positive urine tests are to be confirmed by serum test) documented within the 24-hour period prior to the first dose of study drug.
- Sexually active women of childbearing potential enrolled in the study must agree to use 2 forms of accepted methods of contraception during the course of the study and for 6 months after their last dose of study drug. Effective birth control includes (a) intrauterine device **plus** 1 barrier method; (b) on stable doses of hormonal contraception for at least 3 months (eg, oral, injectable, implant, and transdermal) **plus** 1 barrier method; or (c) 2 barrier methods. Effective barrier methods are male or female condoms, diaphragms, and spermicides (creams or gels that contain a chemical to kill sperm); or (d) a vasectomized partner.
- 8. For male subjects who are sexually active and are partners of premenopausal women: agreement to use two forms of contraception as in criterion 7 above during the treatment period and for at least 6 months after the last dose of study drug, unless the male subject had a vasectomy.
- 9. Capable of understanding and complying with the protocol and has signed the informed consent form.

4.2. Exclusion Criteria

Subjects meeting any of the following criteria will be excluded from participation.

- 1. Previous partial or total nephrectomy or a kidney transplant.
- 2. Tuberous sclerosis, Hippel-Lindau disease, or acquired cystic disease.
- 3. Congenital absence of 1 kidney and/or need for dialysis or transplantation in the foreseeable future.
- 4. Moderate hematuria. Subjects with microhematuria may be enrolled, unless microhematuria is suspected to be due to infection or recent cyst rupture. If hematuria is due to cyst rupture, the subject may be rescreened after discussion with the Medical Monitor.
- 5. Uncontrolled hypertension (systolic blood pressure > 160 mmHg; diastolic blood pressure > 100 mmHg) while receiving antihypertensive therapy.
- 6. Uncontrolled diabetes mellitus (glycated hemoglobin > 8%).
- 7. Presence of renal or hepatic calculi (stones) causing symptoms.
- 8. Received any investigational therapy within 30 days prior to initiation of therapy (Day 1).
- 9. Received tolvaptan within 30 days prior to initiation of therapy (Day 1).

- 10. Received active treatment (within 4 weeks of initiation of therapy [Day 1]) for urinary tract infection.
- 11. History of pancreatitis or known risk factors for pancreatitis.
- 12. Subject meets any of the following cardiac criteria:
 - Mean QTc interval corrected for heart rate using Fridericia's formula (QTcF) of > 450 msec.
 - History of torsade de pointes, ventricular tachycardia or fibrillation, pathologic sinus bradycardia (< 50 bpm), heart block (excluding first-degree block, being PR interval prolongation only), congenital long QT syndrome or new ST segment elevation or depression or new Q wave on ECG. Inclusion of subjects with a history of atrial arrhythmias should be discussed with the Medical Monitor.
 - Family history of congenital long QT syndrome or unexplained cardiac death.
 - History of ventricular rhythm disturbances.
 - Symptomatic heart failure (per New York Heart Association guidelines), unstable angina, myocardial infarction, or cerebrovascular accident within 6 months prior to study entry.
 - Has a cardiac pacemaker.
 - History of pericardial effusion or presence of pericardial effusion on screening echocardiogram
- 13. Subject is taking any medication known to inhibit the CYP3A4 isozyme or any drugs that are CYP3A4 inducers, or any drugs associated with torsade de pointes or known to prolong the QTcF interval, including anti-arrhythmic medications within 2 weeks prior to screening. A stable regimen (≥ 4 weeks) of antidepressants of the selective serotonin reuptake inhibitor (SSRI) class is allowed (common SSRIs include escitalopram oxalate, citalopram, fluvoxamine, paroxetine, sertraline, and fluoxetine).
- 14. Uncontrolled intercurrent illness that would limit compliance with study requirements including, but not limited to ongoing or active infections or psychiatric illness.
- 15. Subject is pregnant, plans to become pregnant, or nursing.
- 16. Known to be positive for the human immunodeficiency virus or hepatitis B or C, as indicated by a positive test at screening.
- 17. Known to be immunocompromised.
- 18. Documented presence of renal vascular disease resulting in uncontrolled hypertension.
- 19. Has previously received an EGFR inhibitor (including, but not limited to, erlotinib, gefitinib, osimertinib, afatinib, cetuximab, panitumumab, or an investigational agent).
- 20. Allergy or hypersensitivity to components of either tesevatinib, matched placebo, or their formulations.
- 21. Aphakic due to previous cataract surgery or congenital abnormality.

Note: The sponsor has the option to exclude a subject from enrollment, if, based upon the subject's medical history or screening results, it is felt that a subject's safety may be at risk and/or if the safety data may confound the study results.

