- 13. Subject is taking any medication known to inhibit the cytochrome P450 (CYP)3A4 isozyme or any drugs that are CYP3A4 inducers, or any drugs associated with torsade de pointes or known to prolong the QTcF interval, including anti-arrhythmic medications within 2 weeks prior to screening. A stable regimen (≥ 4 weeks) of antidepressants of the selective serotonin reuptake inhibitor (SSRI) class is allowed (common SSRIs include escitalopram oxalate, citalopram, fluvoxamine, paroxetine, sertraline, and fluoxetine).
- 14. Uncontrolled intercurrent illness that would limit compliance with study requirements including, but not limited to ongoing or active infections or psychiatric illness.
- 15. Subject is pregnant, plans to become pregnant, or nursing.

16. Known to be positive for the human immunodeficiency virus or hepatitis B or C, as indicated by a positive test at screening.

- 17. Known to be immunocompromised.
- 18. Documented presence of renal vascular disease resulting in uncontrolled hypertension.
- 19. Has previously received an epithelial growth factor receptor (EGFR) inhibitor (including, but not limited to, erlotinib, gefitinib, osimertinib, afatinib, cetuximab, panitumumab, or an investigational agent).
- 20. Allergy or hypersensitivity to components of either tesevatinib, matched placebo, or their formulations.
- 21. Aphakic due to previous cataract surgery or congenital abnormality.

Note: The sponsor has the option to exclude a subject from enrollment, if, based upon the subject's medical history or screening results, it is felt that a subject's safety may be at risk and/or if the safety data may confound the study results.

Maximum duration of subject involvement in the study:

The planned duration of the screening period is no more than 28 days prior to dosing (42 days for MRI and ocular assessments). The planned duration of treatment period is approximately 730 days (or 24 months). The follow-up period will be 30 days from the last dose of study drug.

Endpoints and statistical analysis:

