Informed consent	>					
Medical and PKD history (include genotype, if available)	*					
Physical examination ^d (including weight)	~	~	~	~	~	~
Vital signs ^e	~	~	~	~	~	~
Supine 12-lead ECG ^f	~	~	~	~	~	~
Clinical laboratory tests ^g	~	~	~	~	~	~
Ocular evaluation ^h	>				•	>
Echocardiogram ⁱ	>			~	~	~
Pregnancy test ^j	>	~		~	~	~
MRI ^k	•				(every 6 months beginning at Month 12)	•
Randomization		~				
Study drug/placebo dispensed		~	~	*	~	>
Record adverse events	>	~	~	~	~	~
Record concomitant medication	>	~	~	*	•	>
Drug compliance/collection ¹		~	~	~	~	~

Abbreviations: ECG, electrocardiogram; MRI, magnetic resonance imaging; PKD, polycystic kidney disease; QTc(F), QT interval corrected for heart rate using Fridericia's formula; TSH, thyroid stimulating hormone

- a. Screening evaluations may be combined with Day 1 pre-treatment laboratory evaluations if both are done within 4 days before first dose of study drug. Screening MRI and ocular assessments may be performed up to 6 weeks prior to Day 1.
- b Follow-up treatment period visits to be performed monthly (every 28 ± 1 day). For those subjects continuing on study beyond 12 months, visits will occur every 2 months ± 3 days between Months 12 and 24.
- c. The End-of-study visit is to be performed 30 days (± 3 days) after last dose of study drug.
- d. A complete physical examination is to be done at the Screening and End-of-study visits. Height will only be measured at Screening. Symptom-driven physical examinations will be performed on Days 1, 14, 28, every 28 days from Months 2 to 12, and every 2 months from Months 12 to 24. See Section 7.5.1 for a description of the body systems and evaluations to be performed at each visit (eg, cardiac tamponade, ocular toxicity and xerostomia assessments).
- e. Vital sign measurements will include sitting blood pressure, heart rate, respiratory rate, and oral or tympanic temperature. On Day 1, measurements should be performed predose and 1 and 4 hours postdose. See Section 7.5.2 for details on vital signs measurement.

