- k. Screening MRI will be performed after informed consent form has been signed and prior to other screening assessments. Magnetic resonance imaging will be performed at Month 12, 18, and 24, and at the End-of-study visit
- 1. Subject diaries will be dispensed on Day 1 and reviewed/collected at each visit.

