7. STUDY PROCEDURES

7.1. Study Schedule

The schedule of assessments for this study is provided in Table 2.

All screening assessments are to be performed within 28 days prior to the first dose of study drug, unless otherwise specified. Study eligibility will be based on satisfying all of the study inclusion and exclusion criteria. Day 1 is defined as the date the subject takes the first dose of study drug.

A screen failure is a subject who has given informed consent and failed to meet the inclusion and/or meet at least 1 of the exclusion criteria and has not been randomized or administered investigational product(s) as defined by the protocol.

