9.10. Efficacy Analyses

All efficacy analyses will be based on the Efficacy Population.

The primary efficacy endpoint will be the change from baseline in htTKV at Month 12. An analysis of covariance model including treatment group as a factor and the baseline htTKV as a covariate will be used for efficacy analyses. The Type I error rate will be set at an alpha level of 0.05. Additional efficacy endpoints include change from baseline in htTKV at Months 18, 24, and 30 days post-dose.

In addition, the change in eGFR at the Month 12, 18, 24, and 30-days post-treatment time points will be evaluated.

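### The tolvaptan and investigational-drug washouts run back from Day 1, but the only pre-treatment MRI may be taken up to 42 days before Day 1, so baseline kidney volume can be scanned on an excluded drug

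*Protocol*

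**What the plan says.** Protocol 4.2 has two drug-specific washouts of equal length and with the same reference date. Criterion 8 reads "Received any investigational therapy within 30 days prior to initiation of therapy (Day 1" and criterion 9 reads "Received tolvaptan within 30 days prior to initiation of therapy (Day 1". The synopsis repeats both. Protocol 7.1 fixes the reference date: "Day 1 is defined as the date the subject takes the first dose of study drug".

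The imaging window is longer than the washout. The synopsis sets screening at "no more than 28 days prior to dosing (42 days for MRI and ocular assessments", and Table 2 footnote a agrees: "Screening MRI and ocular assessments may be performed up to 6 weeks prior to Day 1". Footnote k puts the scan at the front of screening: "Screening MRI will be performed after informed consent form has been signed and prior to other screening assessments". The same footnote lists the remaining scans: "Magnetic resonance imaging will be performed at Month 12, 18, and 24, and at the End-of-study visit". No second scan is scheduled before dosing.

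That one scan carries much of the analysis. Protocol 9.10 states: "The primary efficacy endpoint will be the change from baseline in htTKV at Month 12". Its central read is the baseline for that change and the covariate in the primary ANCOVA (SAP 3.9.2). It is also a covariate in the eGFR ANCOVA (SAP 3.9.3) and the first point of the longitudinal htTKV model (SAP 3.10.1). The local read decides eligibility under inclusion criterion 5.

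SAP 3.2.3 takes as baseline the last valid value from the 28 days before first study medication, unless the section on a given assessment says otherwise. The htTKV sections (SAP 2.4.1, 3.9.1 and 3.9.2) do not say otherwise.

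**The concern.** A washout counted from first dose controls what the subject is taking when study drug starts. It does not control what the subject was taking when the baseline MRI was done, because the scan may come first. A subject scanned on Day -42 who takes the last tolvaptan or other trial drug on Day -31 breaks neither criterion, yet the scan precedes that last dose by 11 days.

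If the earlier drug has any reversible effect on kidney volume, that effect enters the baseline and reappears as change from baseline at every later scan. The baseline cannot be retaken once dosing has begun. If the SAP window is applied literally instead, the same subject has no usable baseline and leaves the primary analysis.

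**Working it through.** **1. The plan's own power figure.** Inputs are from Protocol 9.12 and SAP 3.1.2: mean changes of 83.6 and 26.4 mL, SD 90.0 mL, 40 per group, two-sided alpha 0.05.

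- Difference = 83.6 - 26.4 = 57.2 mL.
- Standard error = 90.0 × √(2/40) = 20.12 mL, and 57.2 / 20.12 = 2.842.
- Normal approximation: Φ(2.842 - 1.960) = 0.811. Noncentral t on 78 df: 0.802.

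The stated figure of about 80% reproduces.

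**2. The day windows.** Day -1 is the day before first dose (SAP 3.2.2).

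| Rule | Days covered |
|---|---|
| Washouts, criteria 8 and 9 | Day -30 to Day -1 |
| Permitted screening MRI | Day -42 to Day -1 |
| SAP general baseline window | Day -28 to Day -1 |

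- MRI days not covered by the washout: Day -42 to Day -31, which is 42 - 30 = 12 days. On each of these the scan can fall on or before the last permitted dose (Day -31).
- MRI days outside the SAP window: Day -42 to Day -29, which is 42 - 28 = 14 days. All 12 on-drug days are among them.
- Shortest drug-free interval for a scan inside the SAP window: last dose Day -31, scan Day -28, so 31 - 28 = 3 days.

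A scan on one of the 12 days is therefore a baseline taken on the drug if the protocol window governs. If the SAP window governs, no qualifying baseline exists, and the subject fails the Efficacy Population requirement for a centrally read baseline MRI. Scans from Day -28 onward are off the drug, but possibly by only 3 days.

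**3. Size, on assumed values.** The documents give neither the share of subjects affected nor the size of any carry-over. Suppose a share p in each arm has its change shifted by R mL. The variance becomes 90.0² + p(1 - p)R², and the expected difference between arms is unchanged.

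| p | R (mL) | SD (mL) | t-test power |
|---|---|---|---|
| 0.05 | 10 | √(8100 + 4.75) = 90.03 | 0.801 |
| 0.05 | 60 | √(8100 + 171) = 90.95 | 0.793 |
| 0.20 | 10 | √(8100 + 16) = 90.09 | 0.801 |
| 0.20 | 60 | √(8100 + 576) = 93.15 | 0.774 |

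**4. Chance imbalance.** An excess of 3 affected subjects in one arm of 40 moves the contrast by (3/40) × R. That is 0.75 mL at R = 10 and 4.5 mL at R = 60, or 1.3% to 7.9% of the planned 57.2 mL.

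Steps 3 and 4 are on the mL scale of the sample-size calculation. The primary analysis is an ANCOVA on log10 values, so they indicate order of magnitude only.

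**The case against.** **The SAP already blocks an on-drug baseline.** Read literally, SAP 3.2.3 does not accept a scan from Day -42 to Day -31 as baseline. That is correct, and it means one cannot say flatly that the primary baseline will be an on-drug scan. But the SAP does not cure the problem. It turns a questionable baseline into a missing one, and it conflicts with a 42-day MRI window that the protocol plainly intends. It also leaves the 3-day case untouched.

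**Other provisions might catch these subjects.** Protocol 5.1 requires Medical Monitor approval for additional therapeutic treatment during the study period, and the sponsor may exclude a subject at its option. Either could reduce the number affected. Whether a drug the subject was already taking counts as additional is arguable. The sponsor's option is worded around subject safety and safety data. Neither provision ties the last dose to the MRI.

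**The harm is not documented.** Neither document says that tolvaptan or any investigational drug reversibly changes kidney volume, or that the washouts exist to protect the scan. This stands, and it limits the point to a cheap safeguard.

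**Two stronger readings go too far.** A reader might infer that the gap biases the treatment comparison. Assignment is randomised, so uneven numbers of affected subjects would be chance imbalance, not systematic bias. A reader might also infer that the eGFR endpoint has the same weakness. It does not: laboratory tests are repeated on Day 1 and the SAP takes the last pre-dose value. Table 2 footnote a does let combined screening and Day 1 tests be drawn up to 4 days before dosing, but even that sample is 31 - 4 = 27 days after a Day -31 dose.

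**Conclusion.** The concern holds as a gap in timing and a conflict between documents. The protocol permits the htTKV baseline scan on 12 days when an excluded drug may still be in use, and protocol and SAP disagree on whether such a scan counts. The expected consequence is extra variance, chance imbalance and a distorted covariate. On the assumed range (5-20% of subjects, 10-60 mL), power falls by between 0.001 and 0.028 from 0.802. This is not a threat to the validity of the treatment comparison. It merits a correction because the affected measurement underlies the primary endpoint, cannot be repeated after dosing, and can be protected with little text. The window arithmetic comes directly from the documents; every figure for size rests on assumption.

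**What to change.** 1. Leave exclusion criteria 8 and 9 anchored to Day 1. Moving their anchor to the MRI would be a mistake, because they would then no longer exclude use of these drugs between the scan and first dose, a gap of up to six weeks.
2. Add one sentence to Table 2 footnote k: for a subject who has taken tolvaptan or an investigational therapy, the MRI used as the htTKV baseline is scheduled only after the protocol's own washout interval has elapsed since the last dose.
3. State the htTKV baseline window in the SAP, under 3.2.3 or 3.9, so that it agrees with the protocol's MRI window and no correctly timed scan is lost from the Efficacy Population.

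The cost is a later screening MRI for the few previously treated subjects. Because footnote k places the MRI before the other assessments, screening may also be longer for them. Some could spend longer off their earlier treatment. That is a clinical consequence for the sponsor to weigh when reconciling these passages, and no change to the washout length is suggested here.
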